8.1.2. Analyses for Categorical Data

Categorical endpoints will be summarized by treatment group with the number and percent of subjects at risk in the treatment group within each category.

8.1.3. Analyses for Binary Endpoints

For the differences between treatment groups in the percent of subjects with each Tier-1 AE, an exact method for producing 95% confidence intervals and p-values will be used (Chan and Zhang, 1999). The method is based on inverting two one-sided tests at half the significance level each. As an exact method, it is appropriate for rare events.

For the differences between the treatment groups in the percent of subjects with each Tier-2 AE, an asymptotic method for producing 95% confidence intervals as presented by Miettinen and Nurminen (1985) will be used. As an asymptotic method, it is appropriate for events that are not rare.

8.2. Statistical Analyses

Efficacy analyses, unless otherwise indicated, will be performed according to the intention-to-treat (ITT) principle. Unless otherwise indicated, all efficacy analyses will be done in the FAS.

The Safety Analysis Set (SAS) ... will be used for all safety analyses, unless otherwise specified.

8.2.1. Analysis of Primary Endpoint

The primary objective is to demonstrate superiority of bococizumab over to placebo with respect to the primary endpoint, the time from randomization to the first adjudicated and confirmed occurrence of a major cardiovascular event, a composite endpoint which includes CV death, non-fatal MI, non-fatal stroke, and hospitalization for unstable angina needing urgent revascularization (as defined in [Appendix 1.2](#)). Subjects who discontinue randomized study medication prematurely and have not withdrawn consent will continue to be followed in the study to assess the occurrence of endpoints. Subjects who do not experience any of the components of the primary endpoint will be censored on the date of last contact or 01November2016, whichever comes first. The date of last contact is defined as the date of death, if the date is not missing. Otherwise, the date of last contact is defined as the study discontinuation date, the date of last visit, the date of last telephone contact, the onset date of the last AE, or the randomization date, whichever occurs last.

Primary analysis

The primary endpoint will be analyzed in the FAS using a log rank test stratified by geographic region and LDL-C at the pre-screening visit (<100 mg/dL, ≥100 mg/dL). The overall alpha level for this trial is 0.05. The two-sided alpha level for this log rank test will be adjusted for DMC reviews of all-cause death (see [Section 3](#)), resulting in a two-sided alpha of 0.049.

Analyses supportive of the primary analysis

A Cox proportional hazards model will be fit with the treatment group as a covariate and geographic region and LDL-C at the pre-screening visit (<100 mg/dL, ≥100 mg/dL) as stratification factors. If the model fitting fails to converge, LDL-C at pre-screening will be removed as a stratification factor. The hazard ratio will be presented along with a 95% confidence interval. The goodness of fit of the Cox proportional hazards regression model will be assessed by visual inspection of Arjas plots. Kaplan-Meier estimates of time to first major cardiovascular event will be plotted.

Sensitivity analyses

It is assumed that there will *be a premature study discontinuation rate of 1% per year.*

In order to aid in the assessment of the impact of premature discontinuation from the study on the primary analysis, time from randomization to premature discontinuation from the study will be analyzed. The p-value from a log rank test stratified by geographic region and LDL-C at the pre-screening visit (<100 mg/dL, ≥100 mg/dL) will be presented. A Cox proportional hazards model will be fit with treatment group as a covariate and geographic region and LDL-C at the pre-screening visit (<100 mg/dL, ≥100 mg/dL) as stratification factors. If the model fitting fails to converge, LDL-C at pre-screening will be removed as a stratification factor. The hazard ratio and a 95% CI will be presented.

The impact of informative censoring on the primary analysis of the primary endpoint only will be evaluated through multiple imputations. Imputation will be done for all surviving subjects who were administratively censored and did not have a primary endpoint event. Separate imputation models will be fit for subjects on bococizumab and subjects on placebo.

Imputation for both bococizumab and placebo subjects will use the placebo imputation model under the conservative assumption of switch-to-control risk following premature discontinuation from the study.

Weibull regression models will be fit separately by treatment group. Following Rubin (1987), a completed imputed data set will be generated in two stages. First, parameters for the Weibull model will be generated from a multivariate normal distribution with mean equal to the maximum likelihood estimates (MLE) of the parameters, and the variance-covariance matrix equal to the variance-covariance matrix of the MLE. Second, the Weibull distribution based on the generated parameters will be used to simulate a time to event for each subject requiring imputation conditional on the time of censoring, appropriate treatment group, and baseline age, gender, body mass index, geographic region, LDL-C at the pre-screening visit (<100 mg/dL, ≥ 100 mg/dL), baseline smoking status, baseline history of MI, baseline history of coronary revascularization, baseline history of coronary heart disease, baseline history of diabetes (Type I or Type II), baseline history of heFH or LDL-C ≥ 190 mg/dL, baseline history of stroke, baseline history of congestive heart failure and baseline history of chronic kidney disease.

If an imputed time to event would put the event date after 01November2016, the event will be censored and the imputed event time will be truncated so that the time to event is on 01November2016.

The completed data sets will be analyzed with the Cox proportional hazards model used for the primary analysis. This will be repeated for 100 data sets and the estimates of the log hazard ratio and their standard errors will be combined to form point estimates and confidence intervals using standard multiple imputation methodology (Rubin, 1987). The MI-based estimates and their confidence intervals will then be back-transformed to the hazard ratio scale. The estimated hazard ratio and a 95% confidence interval will be reported.

The reasons for censoring for the primary endpoint will be summarized by treatment group.

Supplemental analyses

Investigator-reported potential primary endpoint events will be listed.

The number and percent of each component of the primary endpoint that occurs first will be summarized by treatment group.

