Cox proportional hazards regression is a semiparametric method for comparing hazard functions under the assumption of proportional hazards. The methodology can include adjustments for covariates for important prognostic factors, produces a point and interval estimate of the treatment effect, and allows for different baseline hazard functions in different strata to reflect different event rates in different strata. The methodology assumes that the censoring function is independent of the hazard function.

The goodness of fit of the Cox proportional hazards regression models for the primary endpoint and key secondary composite endpoint of cardiovascular death, non-fatal MI or non-fatal stroke will be assessed by plots of the cumulative expected number of events (estimated cumulative hazard rates) versus the observed cumulative number of events for each treatment arm within each stratum formed by the combination of the two stratification factors, using the method proposed by Arjas (1988). Departures from straight lines indicate a departure from proportional hazards, which may or may not affect the interpretability of the treatment effect.

Kaplan-Meier estimates

Kaplan-Meier estimates of time to first event will be plotted for the primary endpoint, the key composite secondary endpoint of cardiovascular death, non-fatal MI and non-fatal stroke, and for all-cause death.

Kaplan-Meier estimates are non-parametric estimates of the distribution of time to first event that incorporates information about censoring. The methodology assumes that the censoring function is independent of the hazard function.

Multiple imputations for Cox proportional hazards regression

The impact of informative censoring on the primary analysis will be evaluated through multiple imputations. Imputation will only be done for surviving subjects who discontinued from the study prematurely and did not have a primary endpoint event. Several imputation models for informative censoring will be used. The Weibull distribution will be used to generate the imputed values.

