8.2.5. Summary of Efficacy Analyses

Table 2. Tabular Summary of Efficacy Analyses

Endpoint	Analysis Set	Statistical Method	Covariates/ Strata	Objective
Time to major cardiovascular event	FAS	Log rank test	Geographic region, LDL-C at the pre-screening visit (<100 mg/dL, ≥100 mg/dL)	Primary analysis
		Cox proportional hazards regression	Treatment group/ geographic region, LDL-C at the pre-screening visit (<100 mg/dL, ≥100 mg/dL)*	Decision on primary objective
		Plot of Kaplan-Meier Estimates		Support of primary objective
		Arjas plot	Geographic region × complete statin intolerance	
Time to premature discontinuation from the study	FAS	Log rank test	Geographic region, LDL-C at the pre-screening visit (<100 mg/dL, ≥100 mg/dL)	Impact of premature discontinuation from the study
		Cox proportional hazards regression	Treatment group/ geographic region, LDL-C at the pre-screening visit (<100 mg/dL, ≥100 mg/dL)*	
Time to major cardiovascular event	FAS	Multiple imputations for Cox proportional hazards model	Cox model: Treatment group/geographic region Imputation model: Treatment group, age, gender, BMI, geographic region, LDL-C at the pre-screening visit (<100 mg/dL, ≥100 mg/dL), baseline smoking status, baseline history of MI, baseline history of coronary revascularization, baseline history of coronary heart disease, baseline history of diabetes, baseline history of HeFH/LDL-C≥190 mg/dL, baseline history of stroke, baseline history of congestive heart failure baseline history of chronic kidney disease.	Impact of informative censoring under the switch-to-control assumption

Endpoint	Analysis Set	Statistical Method	Covariates/ Strata	Objective
Time to CV death, non-fatal MI or non-fatal stroke	FAS	Log rank test	Geographic region, LDL-C at the pre-screening visit (<100 mg/dL, ≥100 mg/dL)	First key secondary endpoint; tested only if primary objective met
		Cox proportional hazards regression	Treatment group/ geographic region, LDL-C at the pre-screening visit (<100 mg/dL, ≥100 mg/dL)*	Decision on secondary objective
		Plot of Kaplan-Meier Estimates		Support of secondary objective
		Arjas plot	Geographic region × complete statin intolerance	
Time to all-cause death, non-fatal MI, non-fatal stroke, or hospitalization for unstable angina needing urgent revascularization	FAS	Log rank test	Geographic region, LDL-C at the pre-screening visit (<100 mg/dL, ≥100 mg/dL)	Second key secondary endpoint; tested only if primary objective met

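### SAP 8.2.1 and 8.1.1.1 impute for different subjects in the same informative-censoring analysis; on the ordinary reading the 8.2.1 set yields no imputed events, and Table 2 drops a stratum from its Cox model

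*SAP*

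**What the plan says.** SAP 8.1.1.1, under multiple imputations, defines the subjects as follows: "Imputation will only be done for surviving subjects who discontinued from the study prematurely and did not have a primary endpoint event".

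SAP 8.2.1, under sensitivity analyses, describes the same analysis of the primary endpoint and gives another set: "Imputation will be done for all surviving subjects who were administratively censored and did not have a primary endpoint event". It then applies the placebo Weibull model to both arms "under the conservative assumption of switch-to-control risk following premature discontinuation from the study". Event times are simulated conditional on each subject's censoring time, and a truncation rule follows: "If an imputed time to event would put the event date after 01November2016, the event will be censored". Event-free subjects are censored at the earlier of last contact and 01November2016 (SAP 7 and 8.2.1).

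For the completed data, SAP 8.2.1 says: "The completed data sets will be analyzed with the Cox proportional hazards model used for the primary analysis". That model is stratified by geographic region and pre-screening LDL-C. The multiple-imputation row of Table 2 (SAP 8.2.5) gives "Cox model: Treatment group/geographic region".

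On the number of models, SAP 8.1.1.1 says "Several imputation models for informative censoring will be used", while Table 2 lists one objective: "Impact of informative censoring under the switch-to-control assumption".

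**The concern.** The two sections name different subjects for one analysis. The word *only* in 8.1.1.1 means that the 8.2.1 set cannot be read as an addition to it.

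The 8.2.1 set also defeats the purpose of the analysis if its key term has its usual meaning. Subjects censored because the study closed have no unobserved follow-up before the close, so there is nothing to impute for them. A programmer working from 8.2.1 would report a switch-to-control hazard ratio identical to the observed one, and a reader could take that agreement as evidence of robustness.

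Nothing else in the SAP fills the gap. The time-to-discontinuation analysis and the table of reasons for censoring describe the dropout; neither re-estimates the primary hazard ratio under an alternative assumption about it.

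**Working it through.** The plan gives no figure for this analysis, so there is none to reproduce. The check has three parts.

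**1. The 8.2.1 set under the SAP's own rules.** Let C be the censoring date and T the imputed event date.

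- T is drawn conditional on T > C.
- On the ordinary reading of *administratively censored*, C = 01November2016.
- Hence T > 01November2016 for every such subject, and the truncation rule re-censors each one at 01November2016.

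Imputed events = 0, whatever the Weibull parameters. All 100 completed data sets equal the observed data, between-imputation variance is 0, and the pooled estimate is the unimputed Cox fit. Simulation with Weibull shapes 0.8, 1.0 and 1.2 and maximum follow-up of 1, 2 and 3 years kept 0 imputed events in every data set, from about 16,200 to 16,700 such subjects.

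**2. The intended set (premature discontinuers).** Inputs:

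- 8,500 per arm; placebo event rate 0.023 per year; discontinuation d = 0.01 per year (Protocol 9.1 and 9.1.2; SAP 8.2.1 repeats the 1%).
- Hazard ratio 0.8 (Protocol 9.1), so the bococizumab rate is 0.8 × 0.023 = 0.0184 per year.
- Time from randomization to 01November2016, τ: not given in the documents, so a range is assumed.

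With constant hazards h (event) and d, per subject and averaged over τ:

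- discontinuers = ∫₀^τ d·exp(−(h+d)u) du
- lost person-years = ∫₀^τ d·exp(−(h+d)u)·(τ−u) du
- imputed events = ∫₀^τ d·exp(−(h+d)u)·[1−exp(−0.023(τ−u))] du, with the placebo rate in both arms
- observed events = ∫₀^τ h·exp(−(h+d)u) du
- hazard ratio after imputation = ratio of (observed + imputed events) / (observed + lost person-years)

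| Assumed accrual up to the cutoff | Discontinuers | Lost person-years | Imputed events | HR (from 0.800) |
|---|---|---|---|---|
| Uniform over 2.5 years | 207 | 174 | 3.9 | 0.802 |
| Protocol 9.1 pattern (half in last ten months), cut at 3.1 years | 197 | 188 | 4.3 | 0.802 |
| Uniform over 3.18 years (from original protocol date, 26 August 2013) | 262 | 280 | 6.3 | 0.802 |

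Hand check of the first row:

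- Imputed events: 174 × 0.023 ≈ 4.0.
- The bococizumab arm has about half the lost time, 87 person-years. Charging it the placebo rate adds 87 × (0.023 − 0.0184) = 0.40 events.
- Observed events total 429, so about 429 × 0.8/1.8 = 191 are on bococizumab. Events that would have occurred in the lost time at that arm's own rate: 87 × 0.0184 = 1.6.
- Relative change: 0.40/(191 + 1.6) = 0.0021, so the hazard ratio is 0.800 × 1.0021 = 0.802.
- SE of the log hazard ratio: 2/√429 = 0.097, so the shift is 0.0021/0.097 = 2% of one SE. Across the three rows it is 2–3%.

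A simulation of 200 trials for the first row gave means of 208 discontinuers, 173 lost person-years and 4.0 imputed events. At the planned 4.8 years the same formulas give 16.9 imputed events and a hazard ratio of 0.803.

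The documents give no discontinuation rate other than 1%. At an assumed d = 0.05, the three rows give 19 to 31 imputed events and a shift of 0.008 to 0.010 (0.015 at 4.8 years).

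**3. The Cox model for the completed data.**

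| Place | Strata |
|---|---|
| SAP 8.2.1, model for the primary endpoint | Region, pre-screening LDL-C |
| SAP 8.2.1, completed-data model | Same as above, by reference |
| SAP Table 2, other Cox rows | Region, pre-screening LDL-C, with the non-convergence asterisk |
| SAP Table 2, multiple-imputation row | Region only, no asterisk |

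The Table 2 row is the outlier.

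**The case against.** The strongest reply is that the undefined term could cover everyone alive and censored for whatever reason. Subjects censored at the close would then add nothing because of the truncation rule, the imputed events would come from subjects censored earlier, and 8.2.1 would match 8.1.1.1 in effect. The switch-to-control sentence, and the SAP 1.1 account of the change, point to premature discontinuers as the intended set. This makes the intent fairly clear, but it does not rescue the text. It is not the usual meaning of the term, it still conflicts with *only* in 8.1.1.1, and the same edit is needed.

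A second reply is that the effect is negligible at 1% per year. That is correct and stands. But the analysis exists to test departures from the planned dropout, so the planned rate cannot justify leaving it ambiguous.

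A third concerns Protocol 6.5.2, under which nobody counts as lost to follow-up until the study is completed. A subject silent well before the cutoff might then not be recorded as a premature discontinuer. This largely falls away: date of last contact is the latest of several dates, including the study discontinuation date, so a late discontinuation date moves censoring to the cutoff.

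It is also fair that Table 2 is only a summary and that the body text settles the strata. The promise of several imputation models, and the bococizumab Weibull model that 8.2.1 fits but does not use, are leftover wording and do not carry the point.

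**Conclusion.** The concern holds. SAP 8.1.1.1 and 8.2.1 define the imputed subjects differently. On the ordinary reading the 8.2.1 definition gives exactly zero imputed events; that result rests on the meaning of *administratively censored* and on no rate assumption. If the sponsor meant a broader set, the fault is one of wording. The Table 2 omission stands either way.

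The numerical stake is small: about 4 to 6 imputed events and about 0.002 on the hazard ratio at the planned 1% per year, and 0.008 to 0.010 at an assumed 5%. These figures assume constant hazards, a true hazard ratio of 0.8, full enrollment of 17,000 by the cutoff under the accrual patterns shown, and no non-cardiovascular death. The primary log rank test, its 0.049 alpha and the decision rule are untouched. It should be fixed because a pre-specified sensitivity analysis that can come out empty gives false reassurance.

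**What to change.** - In SAP 8.2.1, replace the sentence defining the imputed subjects with the one in 8.1.1.1, adding that these subjects were censored before 01November2016. The added condition only clarifies: anyone censored at that date contributes no imputed event.
- In the multiple-imputation row of Table 2, add pre-screening LDL-C (<100, ≥100 mg/dL) as a stratum of the Cox model, with the non-convergence asterisk used in the other Cox rows.
- Align the statement in 8.1.1.1 about several imputation models with the single switch-to-control model in 8.2.1 and Table 2, and state whether the bococizumab Weibull model is used.

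The cost is SAP wording and one table cell. No new data are needed, and no programming beyond the flag that selects the subjects. The SAP is to be final before sponsor unblinding, so the change belongs there.

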8.2.2. Analysis of Secondary Endpoints

The secondary endpoints for clinical outcomes include the times from randomization to the first occurrence of the adjudicated and confirmed clinical endpoints described below. Time to each of these endpoints will be tested in the FAS with a log rank test stratified by geographic region and LDL-C at the pre-screening visit (<100 mg/dL, ≥100 mg/dL). For the key secondary endpoints, a fixed sequence testing procedure using the sequence indicated in [Section 4.2](#) will be used with a two-sided $\alpha=0.049$. For other secondary endpoints, and for analyses of the key secondary endpoints other than the log rank test, a two-sided $\alpha=0.05$ will be used. A Cox proportional hazards regression model for each endpoint will be fit with treatment group as a covariate and geographic region and LDL-C at the pre-screening visit (<100 mg/dL, ≥100 mg/dL) as stratification factors. If the model fitting fails to converge, LDL-C at pre-screening will be removed as a stratification factor. The hazard ratio, and a 95% confidence interval will be reported. The goodness of fit of the Cox proportional hazards regression model for the composite endpoint of cardiovascular death, non-fatal MI or non-fatal stroke will be assessed by visual inspection of Arjas plots. For the key secondary composite endpoint of cardiovascular death, non-fatal MI or non-fatal stroke, and for all-cause death, Kaplan-Meier estimates of time to first event will be plotted.

The reasons for censoring the key secondary composite endpoint of cardiovascular death, non-fatal MI and non-fatal stroke will be summarized by treatment group.

Key secondary endpoints

The key secondary endpoints (as defined in [Appendix 1.2](#)) are the times from randomization to the first adjudicated and confirmed occurrence of:

- A composite endpoint of CV death, non-fatal MI, and non-fatal stroke;
- A composite endpoint of all-cause death, non-fatal MI, and non-fatal stroke, and hospitalization for unstable angina needing urgent revascularization;
- A composite endpoint of all-cause death, non-fatal MI and non-fatal stroke;
- Hospitalization for unstable angina needing urgent revascularization.

Other secondary clinical endpoints

Other clinical secondary endpoints (as defined in [Appendix 1.2](#)) are the times from randomization to first adjudicated and confirmed occurrence of:

- A composite endpoint of CV death, non-fatal MI, non-fatal stroke, and hospitalization for unstable angina;
- CV death;
- Any MI (fatal and non-fatal);

- Fatal MI;
- Non-fatal MI;
- Any stroke (fatal and non-fatal);
- Any stroke (fatal and non-fatal) of any etiology;
- Fatal stroke;
- Non-fatal stroke;
- Hospitalization for unstable angina;
- Hospitalization for congestive heart failure (CHF);
- Any coronary revascularization procedure;
- CABG;
- PCI;
- Any arterial revascularizations;
- All-cause death.

Adjudicated and confirmed causes of all-cause death will be tabulated by treatment group in the FAS. The tabulation will include the event rates and 95% confidence intervals. Causes of all-cause death will be classified according to the Adjudication Committee Charter.

The number and percent of the component that occurs first for the key secondary composite endpoints of cardiovascular death, non-fatal MI or non-fatal stroke will be summarized by treatment group.

Investigator reported potential secondary endpoint events will be listed.

Circulating biomarker secondary endpoints

Percent changes from baseline in all lipid endpoints and hs-CRP and nominal changes from baseline in LDL-C will be analyzed using a mixed model repeated measures (MMRM) model with fixed effects for treatment (categorical variable), scheduled visit time point (categorical variable), baseline value (continuous variable), interaction between baseline value and scheduled visit time point, interaction between treatment and scheduled visit time point, and geographic region (categorical variable) and LDL-C at the pre-screening visit (<100 mg/dL, ≥100 mg/dL). Observations will be assigned to visits using the analysis windows in [Table 3](#).

Restricted Maximum Likelihood (REML) estimation will be used, and the default covariance structure will be unstructured. Due to the slow onset of accrual in this event-driven trial, there will be few observations at the last several time points. One or more of the last visits may be removed to ensure convergence of the model fitting. Also, the geographic region with the fewest observations may be combined with the next smallest region to ensure convergence of the model fitting. This may be done twice. If the model fails to converge with an unstructured covariance matrix, a spatial power covariance will be used. If the model fails to converge with this covariance structure, compound symmetry will be used. Kenward-Roger degrees of freedom will be used. Consistent with MMRM model fitting, no explicit imputation of missing assessments will be performed. Estimates of treatment group means and mean treatment group differences using observed margins at Week 14 and each other visit, corresponding 95% confidence intervals, and p-values for the mean differences will be provided. The least-squares mean treatment group estimates and 95% confidence intervals will be plotted longitudinally as indicated below with an asterisk (*).

For nominal changes from baseline in Lp(a), triglycerides and hs-CRP, the same model will be fit in the same manner for log-transformed data. The data will be log transformed prior to calculating changes. Any zero values will be replaced with 0.0001 to enable taking the logarithm. The estimated treatment group means and corresponding 95% confidence intervals from the analysis of the log-transformed data will be transformed to percent changes for reporting. The estimated treatment group differences will be transformed to the ratio of the mean percent changes and reported with transformed 95% confidence intervals along with untransformed p-values.

The percent changes from baseline to last non-missing post-baseline measurement in LDL-C will be analyzed using an analysis of covariance model with treatment group and baseline value as covariates and geographic region and LDL-C at the pre-screening visit (<100 mg/dL, ≥100 mg/dL) as factors. Least squares means with corresponding 95% confidence intervals, the least-squares mean differences and corresponding 95% confidence intervals, and p-values will be presented. This analysis will not use analysis windows.

Circulating biomarker endpoints include (asterisk indicates that the LS-mean treatment group estimates and 95% CI will be plotted longitudinally):

- LDL-C*;
- Total cholesterol*;
- HDL-C;
- Triglycerides;
- Non-HDL-C*;
- VLDL-C;
- RLP-C;

- Apo-A-I;
- Apo-B*;
- Lp(a);
- hs-CRP.

